# 4.4 Subject Recruitment

When the clinical site coordinator and/or investigator becomes aware of a patient who is potentially eligible for enrollment into the study, patient eligibility will be confirmed, and the study investigator or coordinator will approach the child's parent/guardian and/or the patient (as applicable) to offer participation. Each center will maintain a screening log and complete a REDCap screening/enrollment tool for any participants who are eligible for enrollment, but are not enrolled into the study. These data will be reviewed to assure that each participating center is enrolling subjects without significant bias.

# 4.5 Parental Permission and Child Assent

After determining that a subject is eligible, the site investigator or designee will approach the parent/guardian to offer participation for their child in the study. The parent/guardian will be informed about the objectives of the study and the potential risks and benefits of trial participation. If the parent/guardian refuses permission for their child to participate, then all clinical care will be provided to the child in accordance usual institutional practice. Assent will be obtained for patients meeting age requirements for assent. Informed consent/assent will be obtained in the relatively focused atmosphere of a clinic or similar room rather than the more chaotic pre-operative holding area just before surgery.

#### 4.6 Randomization and Treatment Allocation

A cluster randomized controlled trial (C-RCT) will be conducted to compare the two major neurosurgical treatments for CM+SM, PFDD and PFD. The cluster size is expected to be on average 6 participants per center. In order to participate, PRSRC centers with multiple pediatric neurosurgeons were given the option of complying with the treatment allocation and following a standardized procedure or selecting a single study neurosurgeon for the group. If the latter scenario was chosen, the group had to agree that all CM+SM patients referred to that center must be treated by the study neurosurgeon. For cluster randomization, a computer-generated randomization sequence will be generated independently by the study statistician. All eligible participants within each cluster will then be approached for informed consent for the purposes of data collection for the trial.

#### 5. STUDY INTERVENTIONS

#### 5.1 Interventions, Administration, and Duration

The intervention performed will either be a PFD or PFDD. It will be predetermined, based on cluster randomization, which procedure each center performs on their respective participants. A computer-generated randomization sequence will be generated independently by the study statistician. The surgery will occur in each respective center's operating room. With the exception of uniformly receiving the designated center intervention, all research participants will receive usual clinical care in accordance with institutional practice and judgment. Clinical care will include at a minimum an initial clinical evaluation by a participating pediatric neurosurgeon, surgical treatment (PFDD or PFD) and associated perioperative care, and routine post-operative care with prescribed follow-up clinical assessments at  $\leq 6$  weeks, 3-6 months, and 12 months (+/-2 months = 10-14 months) after surgery. Patients will be given the opportunity to re-consent into a study extension where any visits occurring within 5 years postoperatively will be documented, and the QOL questionnaires may be given annually. Research data will be collected at all stages by trained study research assistants/coordinators with strict oversight by site investigators using standard data collection forms. Neuro-imaging is a critical element of the trial, required both for enrollment and to monitor treatment efficacy. As such, MRI of the brain and cervical and thoracic spine are required prior to surgery. Pre-operative lumbar spine MRI will be left to the discretion of the surgeon. MRI of the cervical and thoracic spine are required 12 months (+/-2 months = 10 - 10 months)14 months) post-operatively. These are required for clinical care of CM+SM patients, regardless of participation in the study, and funding is not requested for these examinations. MRI of the lumbar spine, CT of the brain or cervical/thoracic/lumbar spine, "long cassette" or "scoliosis" Xrays, and/or X-rays of the cervical/thoracic/lumbar spine are not required but, will be reviewed if obtained. In the case where the patient returned outside the window for primary analyses, a secondary analysis will include those visits up to 24 months.

Each center will be informed which arm they have been randomized to before enrollment occurs. Therefore, every potential participant/family will be aware of which procedure would be performed if s/he agreed to participate. If the procedure is not an appropriate fit for a particular patient or, the patient/family is not comfortable with the predetermined procedure, the patient will not be enrolled and they will be offered standard of care treatment by the clinical team at that center

#### 5.2 Handling of Study Interventions

All pediatric neurosurgeons involved in the study have completed both an accredited neurosurgery residency and a 1-year subspecialty fellowship in pediatric neurosurgery at a program accredited by the Accreditation Council for Pediatric Neurosurgery Fellowships (ACPNF) or by The American Osteopathic Association (AOA) and are either certified or eligible for certification by both the American Board of Neurological Surgeons (ABNS) and the American Board of Pediatric Neurological Surgery (ABPNS) or the American Osteopathic Board of Surgery (AOBS). Prior to participating in the study, each pediatric neurosurgeon must submit documentation verifying that s/he performed  $\geq$ 20 PFDD/PFD cases at the level of attending pediatric neurosurgeon *or* that that s/he performed  $\geq$ 5 PFDD/PFD cases in the year preceding the participation in the study; and

3) review two videos showing the study-approved operative technique for PFDD and PFD in stepwise fashion. As detailed in the videos, PFDD and PFD both begin with a midline posterior suboccipital incision extending from the level of the inion inferiorly. Suboccipital craniectomy  $\pm$ cervical laminectomies are performed based upon the level of tonsillar position on the preoperative MRI. The posterior atlanto-occipital membrane and any additional constricting epidural bands are then dissected off the dura and bisected. For PFD, the operation is complete (dural scoring or splitting is permitted), and wound closure is initiated. For PFDD, the dura is then incised and retracted for microsurgical dissection. Intradural maneuvers are performed at the surgeon's discretion based on the intra-operative findings, but may include exploration/fenestration of an arachnoid veil, lysis of adhesions, or tonsillar reduction. Following the intradural dissection, the duraplasty is performed with autologous graft or dural substitute, and the wound is closed in standard fashion. Dural opening without subsequent dural closure is not permitted for PFDD or PFD.

# **5.3 Concomitant Interventions**

5.3.1 Allowed Interventions

Medications or other treatments may be administered per usual institutional clinical practice. PFD or PFDD must follow the procedural guidelines outlined in this protocol.

5.3.2 Required Interventions

There are no required interventions outside of the PFD or PFDD procedure itself.

5.3.3 Prohibited Interventions

PFD or PFDD must be in accordance with the procedural guidelines outlined in this protocol. For the purposes of this study, PFD performed with dural opening but no dural closure is not permitted. Similarly, cases requiring concomitant cervical or occipito-cervical fusion or upfront direct syrinx surgery (syrinx fenestration or shunt) are not permitted.

# **5.4 Adherence Assessment**

Periodic quality assurance checks will be performed primarily via remote monitoring by reviewing a random subset of operative notes at each participating site.

# 6. STUDY PROCEDURES

#### 6.1 Schedule of Evaluation

Assessment	Initial Visit	<6 Weeks Follow-Up Visit	3-6 Month Follow-up Visit	12 Month Follow-up Visit	14 months to 5 years postoperative
Inclusion/Exclusion Criteria	Х				
Cluster Randomization	Х				

Informed Consent Form	Х				
Demographics	Х				
Presenting Symptoms	Х				
Childhood History	Х				
Developmental History	Х				
Allergies	Х				
Concomitant Medications	Х				
Family History	Х				
Social History	Х				
General Exam	Х				
Musculoskeletal Exam	Х				
Initial Radiology	Х				
Diagnosis	Х				
Clinical Course of	Х	Х	Х	X	Optional
Treatment					
Complications	Х	Х	Х	Х	Optional
Pt Status	Х	Х	Х	Х	Optional
CHIP	Х	Х	Х	Х	Required
HUI-3 QOL	Х	Х	X	Х	Required
Follow-up Symptoms		Х	Х	Х	Optional
Follow-up Medications		Х	Х	Х	Optional
Follow-up General Exam		Х	Х	Х	Optional
Follow-up Neurological		X	X	X	Optional
Exam					
Follow-up Musculoskeletal		Х	X	Х	Optional
Exam					
Follow-up Radiology		^	^	Х	Optional
Additional		Х	X	X	Optional
Neurological/Orthopedic					
Exam					

^ Any subsequent pre-operative images (Brain/spine MRI/CT/X-rays) will be shared, including in the following scenarios:

- Revision/redo decompression
- Syrinx shunt or fenestration
- Spinal Fusion

#### **6.2 Description of Evaluations**

6.2.1 Screening Evaluation

Screening evaluations and associated studies for determining eligibility must be completed within 6 months of study entry.

#### **Inclusion** Criteria

- 1) Age  $\leq 21$  years old
- 2) Chiari malformation type I with  $\geq 5$  mm tonsillar ectopia
- 3) Syrinx diameter (recorded as the greatest antero-posterior or transverse diameter) 3-9 mm.
- 4) MRI of the brain and cervical and thoracic spine are required prior to surgery and available to be shared with the DCC

#### **Exclusion Criteria**

- 1) Syrinx  $<3 \text{ mm and/or} \ge 10 \text{ mm}$
- 2) Neuro-imaging demonstrating basilar invagination (position of the superior tip of dens ≥5 mm above Chamberlain's line)
- 3) Neuro-imaging demonstrating clival canal angle  $<120^{\circ}$
- 4) Prior PFD, PFDD, or other surgery at the craniovertebral junction
- 5) CM+SM secondary to other pathology (e.g. a tumor)
- 6) Unable to share pre-decompression MRI of the brain and cervical and thoracic spine
- 7) Patients who do not wish to participate

#### **Consenting Procedure**

Informed consent will be obtained in the relatively focused atmosphere of a clinic or similar room rather than the more chaotic pre-operative holding area just before surgery.

When a clinical site investigator and/or research coordinator identifies a candidate for the study, patient eligibility will be confirmed, and the study investigator or coordinator will approach the individual to offer participation. After a thorough discussion to inform the patient and family of the rationale and objectives of the study and the risks, benefits, and alternatives to participation, written informed consent will be obtained from a parent or legal guardian (patient <18 years of age) or the patient themselves (patient >18 years of age). Additionally, assent will be obtained for patients of appropriate age, according to individual institutional practices. If study participation is declined, then all clinical care will be provided to the child in accordance with institutional practice and judgment. Each center will maintain a log of any individuals who are eligible for enrollment, but are not enrolled in the study. These logs will be reviewed to assure that each participating hospital is enrolling subjects without significant bias. In uncertain cases, adjudication of patient eligibility will be performed by a committee blinded to intervention and outcome and considering only the information available at the time of enrollment. Patients will be offered the opportunity to re-consent to participate in continued data collection for five years post-operatively.

#### 6.2.2 Enrollment, Baseline, and/or Randomization

#### Enrollment

In order to allow participants and their families the opportunity to make an informed decision about participating in the study, the consent and assent shall be reviewed and signed prior to surgery. Enrollment may occur in one of the follow manners: 1) the participant signs the consent (participant 18 years); 2) at least one parent/legal guardian signs the consent (participant less than 18 years old); or 3) participant less than 18 years old co-signs the consent with at least one parent/legal guardian (requires that the participant is able to read the consent and understands and agrees with it; this may vary by the institution's local IRB's guidelines). For those participants who are unable to read and understand the consent, but are able to read, understand, and agree with the assent, that document will be signed based on the IRB guidelines.

#### Baseline Assessments

Baseline assessment data to be collected at the initial visit includes the following: PCORI CER-1503-29700 Version 6 March 01, 2021

- Demographics
- Symptoms
- Childhood History
- Developmental History
- o Allergies
- Concomitant Medications
- o Family History
- Social History
- General Exam
- Neurological Exam
- Musculoskeletal Exam
- o Radiology
  - Brain and cervical and thoracic spine MRI
  - MRI of the lumbar spine, CT of the brain or cervical/thoracic/lumbar spine, "long cassette" or "scoliosis" X-rays, and/or X-rays of the cervical/thoracic/lumbar spine are not required but will be reviewed if obtained.
- o Diagnosis
  - Clinical Course of Treatment
  - PFD or PFDD
- Complications
- o CHIP

0

- HUI-3 QOL
- Patient Status
- Additional Neurological/Orthopedic surgery (if applicable)

#### **Randomization**

Individual trial centers will be randomized to perform either PFDD or PFD. In order to participate, trial centers with multiple pediatric neurosurgeons were given the option of complying with the treatment allocation and following a standardized procedure or selecting a single study neurosurgeon for the group. If the latter scenario was chosen, the group had to agree that all CM+SM patients referred to that center must be treated by the study neurosurgeon. For cluster randomization, a computer-generated randomization sequence will be generated independently by the study statistician before the respective participating site enrolls a participant. All eligible participants within each cluster will then be approached for informed consent for the purposes of data collection for the trial. Each participant/guardian will know the randomized treatment selection at the time of the informed consent process.

6.2.3 Follow-up Visits

Data to be collected at follow-up visits includes the following:

- ≤6 weeks postoperative visit:
  - Clinical Course of Treatment
    - Any orthotics
    - Decompression
    - Any fusion or syrinx surgery
  - Complications

- CHIP (if > 1 visit during this period only collect for  $1^{st}$  visit)
- HUI-3 QOL(if > 1 visit during this period only collect for  $1^{st}$  visit)
- o Patient Status
- o Follow-up Symptoms
- Follow-up Medications
- o Follow-up General Exam
- Follow-up Neurological Exam
- Follow-up Musculoskeletal Exam
- Follow-up Radiology Exam (if applicable)
- o Additional Neurological/Orthopedic Surgery
- 3-6 months postoperative visit:
  - Clinical Course of Treatment
    - Any orthotics
    - Decompression
    - Any fusion or syrinx surgery
  - $\circ$  Complications
  - CHIP (if > 1 visit during this period only collect for  $1^{st}$  visit)
  - HUI-3 QOL (if > 1 visit during this period only collect for  $1^{st}$  visit)
  - Patient Status
  - Follow-up Symptoms
  - Follow-up Medications
  - Follow-up General Exam
  - Follow-up Neurological Exam
  - o Follow-up Musculoskeletal Exam
  - Follow-up Radiology Exam (if applicable)
  - Additional Neurological/Orthopedic Surgery
- 6.2.4 Completion/Final Evaluation

Data to be collected at the final visit (12 +/- 2 months postoperative) includes the following:

- $12 \pm 2$  months postoperative visit:
  - Clinical Course of Treatment
    - Any orthotics
    - Decompression
    - Any fusion or syrinx surgery
  - $\circ$  Complications
  - CHIP (if > 1 visit during this period only collect for  $1^{st}$  visit)
  - HUI-3 QOL (if > 1 visit during this period only collect for  $1^{st}$  visit)
  - Patient Status
  - Follow-up Symptoms
  - Follow-up Medications
  - Follow-up General Exam
  - Follow-up Neurological Exam
  - Follow-up Musculoskeletal Exam
  - Follow-up Radiology Exam

- MRI of the cervical (including craniovertebral junction) and thoracic spine MRI
- MRI of the brain or lumbar spine, CT of the brain or cervical/thoracic/lumbar spine, "long cassette" or "scoliosis" Xrays, and X-rays of the cervical/thoracic/lumbar spine are not required but will be reviewed if obtained.
- o Additional Neurological/Orthopedic Surgery

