#### 7.2 Methods and Timing for Assessing, Recording, and Analyzing Safety Parameters

Complications and adverse events will be captured starting with intra-operative period and will continue for one year postoperatively. Additional surgeries, such as a decompression redo/revision, fusion surgery, anterior/ventral decompression, syrinx shunt, and syrinx fenestration will also have surgical complications and adverse events monitored and recorded for the one year collection period.

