#### $\circ$ Complication $\leq 12$ (+/- 2 months) months after initial PFDD or PFD

- Pseudomeningocele: extradural and/or subcutaneous fluid collection resulting in discomfort or pain, limitation of movement, or CSF leak. Radiological evidence of fluid collection alone is not sufficient for diagnosis of pseudomeningocele.
- CSF leak
- Hydrocephalus: requires external drainage, shunting, or endoscopic 3rd ventriculostomy
- Infection: clinical diagnosis that may include fever, wound drainage, dehiscence, or elevated laboratory parameters in association with antibiotic treatment ± surgical debridement.
- Chemical (or aseptic) meningitis: clinical diagnosis prompting medical treatment (e.g. steroids); lumbar puncture and analysis of CSF cell profile not required but will be tracked if available.
- Cervical instability
- Cerebellar ptosis with intractable headaches
- Need for surgical procedures for complication management ≤12 (+/- 2 months) months after initial PFDD or PFD
  - External drainage for the following:
    - ➢ Hydrocephalus
    - $\succ$  CSF leak
    - Pseudomeningocele
    - > Infection
    - Shunt malfunction/infection
  - Simple over-sewing of wound for CSF leak
  - Surgical revision in operating room for the following:
    - $\succ$  CSF leak
    - ➢ Infection
    - > Pseudomeningocele
  - Lumbar puncture and steroids for the following:
    - Chemical meningitis
    - > True meningitis
  - Implantation of ventriculo-peritoneal or other permanent shunt or endoscopic 3rd ventriculostomy for hydrocephalus.
  - Cervical collar and/or fusion for cervical instability
  - Cerebellopexy for cerebellar ptosis

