7.4 Outcomes

The goal of this study is to supply patients and families with the information about the risks and benefits of PFDD and PFD that *they feel* are most important in making informed clinical decisions. As such, the primary outcome of interest is reduction in harm to patients, measured as surgical complications and/or requirement for reoperation for complication management ≤ 12 (+/- 2 months) months after initial PFDD or PFD. Complications and reoperation are associated with additional pain as well as emotional and psychological stress, longer hospital stays, and lost time from school/work. Secondary outcomes focus on efficacy outcomes and will include: 1) comparison of pre-operative symptoms and neurological deficits at ≤ 6 weeks, 3-6 months, and 12 (+/- 2 months) months after surgery and syrinx size and spinal alignment (coronal and sagittal Cobb angles) at 12 (+/- 2 months) months after surgery. This outcome will be evaluated using the CHIP and the HUI-3 QOL instruments where analyses based on CHIP will be used as the primary results for aim 3 in case CHIP and HUI-3 results do not agree.

Because this is a surgical trial, an Adjudication Committee, consisting of two pediatric neurosurgeons and one pediatric neuroradiologist independent of the design and conduct of the trial, will adjudicate the primary outcome measure. The committee will review the primary endpoint based on a blinded review of clinical notes, data forms and imaging studies. Decisions by the adjudication committee will determine final outcomes. Consensus definitions of CSF-related complications following neurosurgery have been developed [34]. These definitions have been reviewed and approved by the neurosurgeons participating in the study and will be used in this trial. Likewise, the extent of syrinx resolution following surgery will be determined by centralized review of blinded imaging studies. By contrast, treatment failure (i.e. need for revision PFDD or PFD) will be determined individually by the treating surgeon in consultation with the patient/family, since such decisions are inherently subjective and based both on the surgeon's level of concern and the patient's discomfort and relative acceptance to the inherent risks of surgery (either PFD or PFDD).

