Second Chiari surgeries will be analyzed as 1) the proportion requiring a surgical revision and 2) the type of second surgery performed (same or cross-over). The 1-sided confidence interval for the difference in rates between the PFD and PFDD groups will be calculated and compared to the corresponding non-inferiority margins.

Specific Aim 3:

Hypothesis: With fewer surgical complications, PFD will be associated with superior QOL compared with PFDD.

Anticipated Outcome: PFD will have superior QOL and will show improvements in overall QOL over time (≤ 12 months post-operatively (± 2 months)) compared to PFDD. In particular, both physical metrics (evaluated by pain frequency, pain severity and non-pain symptoms) and psychosocial metrics will improve at a higher rate and in a shorter period of time after PFD compared to PFDD.

Secondary outcomes include Treatment Efficacy variables and Quality of Life variables. Continuous variables measured at 3 time points over the 12-month follow-up will be analyzed using longitudinal analysis with linear mixed models including the random cluster effect. Binomial and ordinal data will be analyzed using Mixed Model methods accounting for cluster. In addition, sensitivity analyses will be conducted where the missing data points will be imputed based on the last observation carried forward.

It should be noted that for Aim 3, primary analyses will be based on the QoL exam performed at 10 to 14-month window. A sensitivity analyses will also be performed based on the last QoL exam available at any time \geq 3 months after surgery. Analyses based on the mixed effect model will also be performed where both cluster effect and error terms will be random.

Missing data: Based on PRSRC data and early data from this trial, loss to follow-up rate is expected to be low (<2%). To prevent missing data, we will meet with patients at 1 month, 3-6 months and at 12+/-2 months after the procedure. Every effort, including phone call reminders to patients, will be made to decrease loss to follow-up. Loss to follow-up, missing data, and the reasons leading to loss of follow-up or data will be recorded. In case of missing data, we will impute missing data using different methods. Because of the repeated measures nature of the data, the 'last observation

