7.5.1 Metrics

Primary Outcome: measured as a binary (yes/no) variable. The presence of any of the following items will be considered as a poor outcome (harm to patients):

• Intra-operative Complication

- Vascular injury resulting in dissection or stroke
- Intracranial hemorrhage requiring return to surgery for evacuation
- Neurological injury (new cranial nerve deficit, weakness, sensory loss, bowel or bladder dysfunction)
- Death

• Complication ≤ 12 (+/- 2 months) months after initial PFDD or PFD

- Pseudomeningocele: extradural and/or subcutaneous fluid collection resulting in discomfort or pain, limitation of movement, or CSF leak. Radiological evidence of fluid collection alone is not sufficient for diagnosis of pseudomeningocele.
- CSF leak
- Hydrocephalus: requires external drainage, shunting, or endoscopic 3rd ventriculostomy
- Infection: clinical diagnosis that may include fever, wound drainage, dehiscence, or elevated laboratory parameters in association with antibiotic treatment ± surgical debridement.
- Chemical (or aseptic) meningitis: clinical diagnosis prompting medical treatment (e.g. steroids); lumbar puncture and analysis of CSF cell profile not required but will be tracked if available.
- Cervical instability
- Need for surgical procedures for complication management ≤12 (+/- 2 months) months after initial PFDD or PFD
 - External drainage for the following:
 - > Hydrocephalus
 - ➢ CSF leak
 - Pseudomeningocele
 - ➢ Infection
 - Shunt malfunction/infection
 - Simple over-sewing of wound for CSF leak
 - Surgical revision in operating room for the following:
 - ➢ CSF leak
 - ➢ Infection
 - > Pseudomeningocele
 - Lumbar puncture and steroids for the following:
 - Chemical meningitis
 - True meningitis
 - Implantation of ventriculo-peritoneal or other permanent shunt or endoscopic 3rd ventriculostomy for hydrocephalus.
 - Cervical collar and/or fusion for cervical instability

Secondary Outcomes:

- Treatment Efficacy, measured ≤6 weeks, 3-6 months, and 12 (+/- 2 months) months after surgery:
 - Status of clinical symptoms
 - Status of neurological findings
 - Syrinx diameter (in mm)
 - Spinal alignment (coronal and sagittal Cobb angles)
 - Need for revision of PFDD or PFD
- Quality of life, measured ≤6 weeks, 3-6 months, and 12 (+/- 2 months) months after surgery:

- Chiari Health Index in Pediatrics (CHIP)
- HUI-3.

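### Later direct syrinx surgery has no rule in the syrinx-regression analysis, so a syrinx reduced by a shunt or fenestration can be credited to the assigned decompression

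*Protocol*

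**What the plan says.** **Later syrinx surgery is foreseen and collected.**
- Protocol 5.3.3 states that "upfront direct syrinx surgery (syrinx fenestration or shunt) are not permitted". The bar is on surgery done at the outset, not on surgery during follow-up.
- Protocol 6.2.3 and 6.2.4 list "Any fusion or syrinx surgery" among the data for all three follow-up visits.
- The footnote to the schedule in Protocol 6.1 names "Syrinx shunt or fenestration" among the situations in which pre-operative images are to be shared.
- Protocol 7.2 lists these operations separately from redo decompression: "syrinx shunt, and syrinx fenestration will also have surgical complications and adverse events monitored and recorded for the one year collection period".

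**The outcomes for failure and further surgery cover decompression only.**
- SAP 7.4 defines "treatment failure (i.e. need for revision PFDD or PFD".
- SAP 7.5.1 lists "Need for revision of PFDD or PFD" as the efficacy item, as does Protocol 10.3.3.
- SAP 7.5 says "Second Chiari surgeries will be analyzed as 1) the proportion requiring a surgical revision", and then classifies the second operation as the same type or a cross-over. Its sensitivity analysis with and without second operations is likewise limited to Chiari surgery.
- In the primary harm composite (Protocol 10.3.3, SAP 7.5.1) a permanent shunt counts when placed for hydrocephalus. A syrinx shunt is not named.

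**How syrinx regression is measured.** SAP 1.2 makes clinical symptoms and syrinx regression the primary variables of Aim 2 and takes the visit nearest 12 months when there are several. SAP 7.2 describes regression as a comparison of syrinx size on MRI before and after surgery. SAP 7.4 assigns the reading to blinded central review, and SAP 7.5 sets the margin at 0.135. None of these places says what happens if a shunt or fenestration came before the scan.

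**The concern.** Direct syrinx surgery during follow-up is an intercurrent event that acts on the very quantity being measured. If a syrinx persists after the assigned operation, is then shunted, and is smaller on the 12-month MRI, the stated measurement rule credits the shrinkage to the assigned decompression. No failure outcome records the event either.

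In a superiority comparison this would mostly dilute a difference. In a non-inferiority comparison, dilution helps the new treatment pass. If later syrinx surgery is more common after PFD, the arms move together and PFD can be declared non-inferior on syrinx regression when it is not. A rule for repeat decompression does not close the gap, because the plan treats the two kinds of surgery as separate events.

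**Working it through.** **Inputs**
- PFDD regression rate 89.1%, effective n = 68 per group, margin 0.135, one-sided alpha 0.05, stated power 81% (Protocol 9.5 and SAP 7.2, Aim 2).
- Rate of later syrinx shunt or fenestration by arm: not given in either document. Assumed here at 0 to 5% per arm.

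**Formula.** With unpooled SE = √[p_C(1 − p_C)/n + p_T(1 − p_T)/n], where C is PFDD and T is PFD,

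P(conclude non-inferiority) = Φ{[0.135 − (p_C − p_T)]/SE − 1.645}.

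**Step 1: reproduce the plan's figure.** With both rates at 0.891, SE = √(2 × 0.891 × 0.109/68) = 0.0534. Then 0.135/0.0534 − 1.645 ≈ 0.88 and Φ ≈ 0.811. The stated 81% is reproduced, on the assumption of equal true rates.

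**Step 2: put PFD on the margin.** Count later syrinx surgery as failure and set PFD at 0.891 − 0.135 = 0.756. The chance of concluding non-inferiority is then the nominal 5.0%.

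**Step 3: score the operated children as regressed.** Add the assumed share in each arm to that arm's rate and recompute. Every such child is assumed to be read as regressed at 12 months.

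| Later syrinx surgery, PFD / PFDD | Rates as scored, PFD / PFDD | P(conclude non-inferiority) |
|---|---|---|
| 0% / 0% | 75.6% / 89.1% | 5.0% |
| 1% / 0% | 76.6% / 89.1% | 6.8% |
| 2% / 0% | 77.6% / 89.1% | 9.2% |
| 3% / 0% | 78.6% / 89.1% | 12.2% |
| 5% / 0% | 80.6% / 89.1% | 20.4% |
| 5% / 2% | 80.6% / 91.1% | 12.8% |
| 5% / 5% | 80.6% / 94.1% | 5.0% |
| 0% / 3% | 75.6% / 92.1% | 1.6% |

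Worked line for 3% / 0%: SE = √[(0.891 × 0.109 + 0.786 × 0.214)/68] = 0.0625; the difference is 0.105; (0.135 − 0.105)/0.0625 − 1.645 ≈ −1.165; Φ ≈ 0.122.

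The result is driven mainly by the net excess: 5% against 2% gives nearly the same risk as 3% against none. In counts, 2 to 5 points of 68 is about 1 to 3 children (1.4 to 3.4).

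**Step 4: spinal deformity.** No margin, rate or power is stated for it, so no corresponding figure can be calculated.

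**The case against.** The strongest reply is that the direction is unknown. No rate of later syrinx surgery is given for either arm. The registry figures of 12.3% after PFD and 5.0% after PFDD (Protocol 7.2.1) concern repeat decompression, a different operation that has its own analysis. The sign could even reverse: after PFD a dural opening is still available as the second operation, while after PFDD it has already been done. That is inference too, but it stands as a reason not to assert a bias in favour of PFD. The plan also states no numerical threshold for regression and leaves the reading to central review, so a shunted syrinx counts only if that review finds it smaller. What the reply leaves untouched is that nothing tells the reviewers or the analyst to treat a surgically drained syrinx differently.

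A reader might infer three stronger things that the documents do not support.

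- *That fusion is counted nowhere.* The primary composite includes "Cervical collar and/or fusion for cervical instability". Only fusion for deformity lacks a place.
- *That a curve straightened by fusion yields a false non-inferiority verdict.* SAP 1.2 makes progression of spinal deformity exploratory, and SAP 7.5 gives it no margin, so there is no margin-based verdict to falsify. Nor is progression scoring defined, so it cannot be said that a fused child would be coded as unchanged. Scoliosis at entry is not an exclusion, so a fusion may treat a curve that was already there.
- *That a higher pass rate at the tabulated PFD rate shows error.* At 81.2% against 89.1% the chance of passing is about 24%, and excesses of 2 to 5 points lift it to about 36% to 59%. But the true difference there is 7.9 points, inside the 13.5-point margin, so passing would be the correct conclusion.

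**Conclusion.** The point holds for syrinx regression. Later shunt or fenestration is collected, belongs to no efficacy or failure outcome, and has no rule in a primary Aim 2 comparison. Following the stated measurement can therefore turn a failure of the assigned operation into a success.

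The size is conditional. With true PFD on the margin, 68 per arm and every operated child read as regressed, a net PFD excess of 2, 3 or 5 points raises the false non-inferiority risk from 5% to about 9%, 12% or 20%. Equal rates leave it at 5%, and an excess after PFDD takes it below 5%. The excesses are assumptions. The repeat-decompression figures make an excess after PFD plausible but do not establish it. Because the direction cannot be known in advance, the rule should be fixed before the data are seen by arm.

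For spinal deformity the missing rule is a descriptive weakness only. The change is worth making, but the gap does not undermine the primary harm comparison.

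**What to change.** In SAP 1.2 and 7.5 (Aim 2):

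1. In the primary syrinx analysis, score a child who has a syrinx shunt or fenestration before the 12 ± 2-month MRI as not regressed. This needs no extra scan.
2. Add two sensitivity analyses: one using the last MRI before that operation where available, and one using the 12-month MRI as observed. The first may be incomplete: the Protocol 6.1 footnote says such images will be shared, but the protocol's Interventions and Duration section lists them as not required and reviewed if available.
3. Tabulate later direct syrinx surgery and deformity fusion by arm beside revision decompression.
4. For the exploratory deformity outcome, flag fused children and show results with and without them. Fusion should not count automatically as progression, since it may treat a curve present at baseline.

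The cost is a few sentences in the SAP; the surgery data are already collected. The downside is that the PFD regression rate may look slightly less favourable. Only outcome scoring changes, not care.
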